# Study Protocol

Official Title : Comparison of Operating Conditions, Postoperative Recovery and Overall Satisfaction Between Deep and Restricted Neuromuscular Blockade for Spinal Surgery Under General Anesthesia

Identifiers : NCT02724111

Date of Document : 4th February 2016

Protocol of the Research	
1.1 Objectives & Hypotheses	
* Objectives
 
Primary Outcome Measure(s):
 
 
1. Mean Value of Peak Inspiratory Pressure [Time Frame: Every 15 minutes during anesthesia]
 
 
Secondary Outcome Measure(s):
 
 
2. Mean Value of Pressure of Back Muscle Retractor [Time Frame: Every 15 minutes during the placement of the retractor]
 
3. Overall Satisfaction of Surgeons for the Surgical Condition [Time Frame: After surgery]
 
4. The Muscle Tone [Time Frame: at the screw insertion through the pedicle of spine during surgery]
 
5. The Number of Body Movements [Time Frame: Throughout the surgery]
 
6. The Degree of Bleeding [Time Frame: Throughout the surgery]
 
7. Recovery Time (Time to Reach Sedation Score 5 at Post-anesthesia Care Unit (PACU). [Time Frame: every 10 min for 1 hour at PACU.]
 
8. Adverse Events [Time Frame: during the postoperative 24 hours]
 
 
* Clinical hypotheses
 
 
(1) Mean value of peak inspiratory pressure (PIP) is lower in deep NMB group than in restricted NMB group. The higher PIP in restricted NMB group is related to the more surgical bleeding compared to deep NMB group.
 
(2) Operating conditions including the number of body movement, degree of bleeding and muscle tone in deep NMB group are superior to restricted NMB group.
 
(3) Overall satisfaction of surgeons in deep NMB group is superior to restricted NMB group.
 

1.2 Background & Rationale, Significance of Selected Topic	
Current standard of anesthesia in Motor Evoked Potential (MEP) monitored neurospinal surgeries is TIVA (total intravenous anesthesia) without muscle relaxant or with shallow NMB because deep NMB prevents monitoring of MEPs during surgery.
 
However, there are several disadvantages associated with surgical and anesthetic conditions in MEP monitored surgeries.
 
We aim to investigate operating conditions, postoperative recovery and overall satisfaction of surgeons between deep NMB group and restricted NMB for MEP not monitoring spinal surgery under general anesthesia. We expect that this study can present good surgical conditions, postoperative recovery outcomes and overall satisfaction of surgeons in deep NMB group, thereby proving the advantages of deep NMB as well as flaws of restricted NMB in spine surgeries.
 
In this study, channeling bias is not likely to be problematic, as the establishment of group and the indications or criteria of MEP monitoring in spine surgeries are mainly associated with the patient's clinical signs and pre-existing motor deficits

	
rather than the extent or difficulty of surgery. However, channeling regarding to the group treatment according to MEP monitoring can make this study be a non-randomized trial and certain patient differences would be expected between treatment groups. Therefore, we will enroll patients undergoing spinal surgery without MEP monitoring to determine the value of deep block on surgical and anesthetic condition.


1.3 Study Design
	
Group treatment (Arms): Group RB, group treated restricted NMB; Group DB, group treated with deep NMB → randomized allocation (subjects: MEP not monitored surgeries)
 
Inclusion criteria: Ninety ASA class I-II adults, aged 18-75 years, scheduled for elective spinal surgery (lumbar surgeries which have lesions no more than 3 spinal levels and not monitored by MEP) of duration >1 hour and prone position under TIVA
 
Exclusion criteria: Pregnancy, the receipt of medication known to interfere with neuromuscular blockade, diseases affecting neuromuscular transmission, and the history of hypersensitivity on rocuronium or sugammadex. The patients who will have hemodynamic instability, mean blood pressure increase or fall of > 30% from baseline (lasting for more than 5min), and blood loss > 1 L during surgery, and MEP monitored surgeries.
 
Monitoring devices: An electrocardiograph, pulse oximetry probe, esophageal temperature probe, entropy sensor (Datex Ohmeda) and noninvasive blood pressure cuff or invasive arterial and central vein lines will be applied to patients before or after anesthesia induction. The neuromuscular blockade will be monitored with a train-of-four (TOF, frequency 2 Hz, current 50 mA, interval 15 s) using an accelerator device (TOF-Watch SX; Organon Ltd, Ireland). The stimulation electrodes will be placed on the wrist at the level of the ulnar nerve, and the accelerometer will be placed at the distal part of the thumb. The skin temperature on the patient's thenar will be maintained above 32°C throughout the study by wrapping the arm in cotton. The TOF ratio (T4/T1) and T1 value will be displayed on the screen and recorded. State entropy will be used as a guide for anesthetic depth and it will be maintained at 40 to 60 during surgery.


1.4 Study Flowchart
	<pre> graph TD     A[Patients Enrollment (n=90)] --> B[Group DB (n=45)]     A --> C[Group RB (n=45)]     B --- D["* NMB strategy: - rocuronium 1 mg/kg for induction - maintain deep NMB (TOF count 0, PTC of 1-2)"]     C --- E["* NMB strategy: - rocuronium 1 mg/kg for induction - use of sugammadex to reverse the NMB 10 min after position change (supine → prone) and thereafter, maintain the state of no more use of additional muscle relaxant"]   </pre> 
The flowchart illustrates the study design. It begins with 'Patients Enrollment (n=90)' at the top, which branches into two groups: 'Group DB (n=45)' on the left and 'Group RB (n=45)' on the right. The 'Group DB' box contains the text: '* NMB strategy: - rocuronium 1 mg/kg for induction - maintain deep NMB (TOF count 0, PTC of 1-2)'. The 'Group RB' box contains the text: '* NMB strategy: - rocuronium 1 mg/kg for induction - use of sugammadex to reverse the NMB 10 min after position change (supine → prone) and thereafter, maintain the state of no more use of additional muscle relaxant'.

	
Operation condition assessment
 
1) airway pressure (peak inspiratory pressure)  2) pressure of back muscle retractor  3) the number of body movements  4) the degree of bleeding of each patient scaled by surgeons  5) the muscle tone of each patient scaled by surgeons
 
Reversal of NMB  Sugammadex 4 mg/kg  at the end of the surgery
 
Reversal of NMB  No reversal agent;  but if TOF ratio<0.9  pyridostigmine 10 mg
 
Postoperative assessment
 
 
- recovery time
 
- occurrence of adverse events
 
- overall satisfaction of surgeons
 
	

1.5 Study Procedures
 
* Blinding and measure of outcomes
 
· A double blinded approach will be used in this trial: randomization for group allocation and allocation concealment will be kept in this study. In the operating room, induction and maintenance (including the operation of TOF-Watch) of anesthesia will be performed by independent anesthesiologists not involved in the study and they are not blinded to the group allocation of patients. However, all surgeons will be blinded and so the evaluation of muscle tone of each patient scaled by surgeons will be blinded. Also, after the end of surgery, a blinded, independent investigator will assess the patients during the emergence and recovery phases. Postoperative outcomes including recovery time and surgeon satisfaction will be measured by the investigator blinded to the group assignment.
 
➔ If the patients show any body movement during surgery or if surgeons express any complaint about muscle tone (the muscle tone: grade 3), rescue rocuronium 5 mg will be administered and the number of body movements and rescue rocuronium administration (dose) will be recorded.
 
➔ The extubation criteria are as follows: TOF ratio > 0.9, BIS > 70, regular respiratory pattern, tidal volume of at least 5 ml/kg and SpO2 > 95% when the patient breathes spontaneously.
 
* Drug treatment
 
· Premedication: midazolam 2 mg, i.m (in all patients)
 
· Induction: In all patients, after lidocaine 40 mg, i.v, effect-site concentration (CE) of propofol will be increased stepwise from the initial CE of 2.0 µg/mL until loss of the eyelash reflex (or arrival of state entropy less than 60), and then the TOF-Watch will be calibrated using the automatic calibrating procedure as soon as the patient is asleep. The first response in the TOF sequence (T1) will be defined as the baseline value to which all subsequent responses are compared. Effect-site concentration of remifentanil will be then fixed to 1.5 ng/mL and rocuronium 1 mg/kg will be injected and the patients will be tracheally intubated at arrival of minimum T1 height.
		

	
· Ventilator settings: Tidal volume 8 mL/kg, respiratory rate initially 10 to 12 breaths/min, positive end-expiratory pressure (PEEP) 4 cmH2O and inspiratory-to-expiratory time ratio 1:2. Mechanical ventilation (respiratory rate) will be adjusted to maintain an end-tidal partial pressure of carbon dioxide at between 30 and 35 mmHg during surgery.
 
· Maintenance: The patients will be allocated to one of the 2 groups receiving either DEEP NMB (group DB) or RESTRICTED NMB (group RB) according to the assignment using a computer random number generator.
 
· NMB: In the group DB, rocuronium will be administered to maintain deep NMB (TOF count 0, PTC of 1-2 twitches) until the end of surgery and the reversal of NMB will be performed by sugammadex 4 mg/kg.
 
In the group RB, sugammadex will be administered according to the prescribing indications (4 mg/kg for deep NMB state or 2 mg/kg for moderate NMB or less) to reverse the NMB 10 min after position change (10 min after placing the patient prone). Thereafter, muscle relaxants will not be injected any more throughout the surgery except the following situations: If the patients show any body movement during surgery or if surgeons express any complaint about muscle tone (the muscle tone: grade 3), rescue rocuronium 5 mg will be administered and the number of body movements and rescue rocuronium administration (dose) will be recorded.

1.6 References	
 
Edmonds HL Jr, Paloheimo MP, Backman MH, Johnson JR, Holt RT, Shields CB. Transcranial magnetic motor evoked potentials (tcMMEP) for functional monitoring of motor pathways during scoliosis surgery. Spine (Phila Pa 1976) 1989;14(7):683-6.
 
 
Kalkman CJ, Drummond JC, Kennelly NA, Patel PM, Partridge BL. Intraoperative monitoring of tibialis anterior muscle motor evoked responses to transcranial electrical stimulation during partial neuromuscular blockade. Anesth

Analg 1992;75(4):584-9.

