## Statistical Analysis Plan

1. Statistical Analysis Plan and Sample Size Justification	
* Statistical Analysis Plan
 
Statistical analyses will be performed using SPSS software (SPSS version 20.0, IBM, Chicago, IL, USA).
 
Student's t-test or Mann-Whitney U-test will be used to compare continuous data including the mean values of the peak inspiratory pressure, the pressure of back muscle retractor and recovery time between the groups. Though measurement timepoints of peak inspiratory pressure and pressure of back muscle retractor are multiple, the mean value of each timepoint will be calculated and the mean value of each group will be analysed by Student's t-test.
 
The normal distribution of the continuous data will be first evaluated using the Shapiro-Wilk test (<math>P > 0.05</math>). The normally distributed data will be analysed using the Student's t-test, and the abnormally distributed data will be analysed using the Mann-Whitney U-test.
 
Ordinal variables including, the degree of bleeding of each patient scaled by surgeons, assessed using a 6-point scale and overall satisfaction of surgeons, assessed using numerical rating scale (NRS; 1-10) will be compared using the Mann-Whitney U-test. Categorical variables such as the muscle tone of each patient scaled by surgeons, assessed using a 3-point scale, the number of body movements during the surgery and the incidence of adverse events between the groups will be compared using a chi-squared test (or Fisher's exact test).
 
The data will be expressed as the mean <math>\pm</math> standard deviation, median (25; 75 quartiles), or number of patients (%). P-values will be reported as two-tailed values and a P-value <math>< 0.05</math> will be considered statistically significant.
 
* Sample size calculation
 
Primary endpoint in this study is mean value of peak inspiratory pressure during the surgery. The sample size calculation was based on the results of a pilot study with 10 cases in each group. In the pilot study, peak inspiratory pressure (mean <math>\pm</math> standard deviation) was <math>18.8 \pm 2.9</math> cmH2O in Group DB and <math>20.7 \pm 3.0</math> cmH2O in Group RB, respectively. Therefore, the effect size of 2-groups was 0.64. On the assumption that the allocation ratio of 2-groups was 1, a sample size of 39 patients was selected for each group, calculated by Student's t-test, two-sided test, a level of significance of 0.05 and a power of 0.8. We estimated a 15% drop-out, resulting in the final enrolment of 45 patients in each group (total, 90 patients).

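### Mean PIP is compared without using readings taken before the arms diverge, and the two documents disagree on whether those readings belong in the outcome

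*Protocol*

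**What the plan says.** Protocol 1.1 gives the primary outcome as "Mean Value of Peak Inspiratory Pressure [Time Frame: Every 15 minutes during anesthesia". The SAP, under its sample size heading, words the window differently: "Primary endpoint in this study is mean value of peak inspiratory pressure during the surgery".

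Protocol 1.5 treats all patients alike at induction: "rocuronium 1 mg/kg will be injected and the patients will be tracheally intubated at arrival of minimum T1 height". The ventilator settings are also common to both arms: "Tidal volume 8 mL/kg, respiratory rate initially 10 to 12 breaths/min, positive end-expiratory pressure (PEEP) 4" cmH2O. The first scheduled arm-specific step with a stated time is sugammadex in group RB, given "to reverse the NMB 10 min after position change (10 min after placing the patient prone". Group DB is held in deep block to the end of surgery, but the Protocol does not say when its maintenance rocuronium begins.

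For the analysis, the SAP states: "Student's t-test or Mann-Whitney U-test will be used to compare continuous data including the mean values of the peak inspiratory pressure". It then says that the timepoints are averaged and that "the mean value of each group will be analysed by Student's t-test". I read this as one average per patient, compared between arms. The Shapiro-Wilk result decides between the two tests. No baseline PIP, covariate, change score or repeated-measures model is named.

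**The concern.** At a tidal volume fixed per kilogram, PIP still varies between patients with compliance and airway resistance, whatever the arm. That variation sits in the SDs of 2.9 and 3.0 cmH2O, against an expected difference of only 1.9. A reading from the same patient and ventilator before the arms diverge would measure much of it directly. The schedule should produce such a reading, and the plan does not use it. What is at stake is the precision of the primary comparison.

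The second issue is the outcome window. If the mean runs over the whole anaesthetic, it includes readings taken under the shared induction block, where little or no difference between arms can exist. If it runs over the surgery only, some or all of those readings drop out. The two documents thus describe different primary outcomes.

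**Working it through.** **Inputs (SAP, sample size paragraph).** Pilot of 10 per group; DB 18.8 (SD 2.9) and RB 20.7 (SD 3.0) cmH2O; two-sided alpha 0.05; power 0.80; 39 evaluable per group.

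**Step 1: reproduce the plan's figure.**
- Difference = 20.7 − 18.8 = 1.9.
- Pooled SD = √((2.9² + 3.0²)/2) = 2.95, so d = 1.9/2.95 = 0.644.
- Two-sample t-test, noncentral t, 39 per group: power 0.802. The stated 39 is reproduced, and it rests on the full between-patient SD.

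**Step 2: adjust for a pre-divergence reading.** Let r be the within-arm correlation between baseline PIP and the later mean. The documents give no value, so r is an assumption.
- Residual SD = 2.95 × √(1 − r²).
- Standard error of the difference = residual SD × √(2/39).
- Degrees of freedom = 2 × 39 − 3 = 75, one being spent on the covariate.
- Example, r = 0.5: residual SD = 2.95 × 0.866 = 2.56; SE = 2.56 × 0.226 = 0.58; noncentrality = 1.9/0.58 = 3.28; power 0.90.

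| r (assumed) | Residual SD | Power, 39 per group | 95% CI half-width | Evaluable n per group for 80% power |
|---|---|---|---|---|
| 0 (as planned) | 2.95 | 0.80 | 1.33 | 39 |
| 0.3 | 2.81 | 0.84 | 1.27 | 36 |
| 0.5 | 2.56 | 0.90 | 1.15 | 30 |
| 0.7 | 2.11 | 0.98 | 0.95 | 21 |

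A change from baseline would be less safe. With equal SDs its SD is 2.95 × √(2(1 − r)), and power at 39 per group is 0.66 at r = 0.3, 0.80 at 0.5 and 0.95 at 0.7. At r = 0.3 that is worse than no adjustment, so ANCOVA is the better form.

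**Step 3: dilution under the Protocol's window.** Suppose that 1.9 is the difference after divergence, that a fraction f of readings comes before it, and that the SD stays at 2.95. The expected difference is then 1.9 × (1 − f).
- f = 0.1: 1.71, power 0.71.
- f = 0.2: 1.52, power 0.61.
- f = 0.3: 1.33, power 0.50.

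The fraction f is also an assumption. If the pilot already averaged over the whole anaesthetic, 1.9 is the diluted figure and power stays at 0.80. In that case the difference after divergence is larger, for example 1.9/0.8 = 2.4 at f = 0.2. The documents do not say which window the pilot used.

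**Step 4: would a pre-divergence reading exist?** The period from intubation to RB reversal is the time taken to turn the patient prone plus 10 min. A 15-minute grid is certain to place a reading in it if that first part lasts at least 5 min (5 + 10 = 15). The prone part alone lasts 10 min, less than the interval, so a prone reading before reversal is not guaranteed.

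**The case against.** The strongest reply is that nothing here is an error. Under randomisation an unadjusted t-test on a per-patient mean is valid. The trial was sized on the raw SDs and meets its own power target. Chance imbalance in lung mechanics is ordinary sampling error, already covered by the standard error and alpha. All of this stands. A reader might infer that the planned comparison is biased or underpowered; the documents do not support that if the pilot difference applies to the window analysed.

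A reader might also infer that every patient already has a baseline reading under identical conditions. That goes too far. Neither document names a baseline or says when the 15-minute clock starts, and Step 4 shows that a prone reading is not assured. Identical holds for the induction dose and ventilator settings, but not necessarily for the block just before RB reversal: DB maintenance is not said to wait for that point, and the Protocol allows RB to be at different depths when it is reversed. A reading taken after arm-specific dosing has begun could carry part of the treatment effect, and adjusting for it could remove some of that effect.

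Finally, the gain depends on an unknown r. It is slight at 0.3, tidal volume is already scaled to weight, and a supine baseline may correlate less with later prone readings. These points limit where the baseline can be taken and how much to claim for it. They do not remove the case for taking one, and they leave the conflict between the windows untouched.

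**Conclusion.** The point holds as one of precision and outcome definition. The planned analysis is sound but leaves usable information aside. At 39 per group and a 1.9 cmH2O difference, ANCOVA on a pre-divergence PIP would raise power from 0.80 to about 0.84, 0.90 or 0.98 for assumed correlations of 0.3, 0.5 or 0.7. At r = 0.5 the chance of missing a true 1.9 cmH2O difference falls from 20% to 10%. These figures take 1.9 and 2.95 as applying to an outcome restricted to readings after divergence, which the documents do not confirm.

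The conflict between the two windows does not depend on r and must be resolved whether or not a baseline is added. The change is worth making because it is cheap, but the trial does not fail without it.

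**What to change.** 1. Prespecify one baseline PIP reading in every patient, at a fixed time after intubation and before any arm-specific neuromuscular drug is given. A prone reading before the RB reversal time is preferable only where no DB maintenance rocuronium has yet been given; record the time of the first such dose so that this can be checked.
2. Use one outcome window in both documents: each patient's mean PIP over readings after the RB reversal time, with the same clock point (10 min after prone) in DB.
3. Make the primary analysis an ANCOVA of that mean on arm and baseline PIP, and report the adjusted difference with its 95% CI. For this endpoint it replaces the choice between t-test and Mann-Whitney.
4. State which window the pilot figures refer to.

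The cost is a short SAP revision, a reworded outcome in Protocol 1.1 and one timed reading from the ventilator. No extra patients or equipment are needed, and 39 per group can stand. Because step 2 redefines the primary outcome, it should be settled before any comparison by arm. A missing baseline needs a simple prespecified imputation, and a supine baseline may bring a smaller gain.

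### Muscle tone is tied to pedicle-screw insertion, which eligibility does not require, and grade-3 tone rescued before that moment may go uncounted

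*Protocol*

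**What the plan says.** **Scoring time.** Protocol 1.1, secondary outcome 4, lists one time frame for muscle tone: "at the screw insertion through the pedicle of spine during surgery". The flowchart in 1.4 lists tone among the operating-condition assessments without a time.

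**Eligibility.** Protocol 1.3 admits elective prone procedures of more than one hour, described as "lumbar surgeries which have lesions no more than 3 spinal levels and not monitored by MEP". Fusion, instrumentation and screws are not mentioned.

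**Rescue.** Protocol 1.5, under blinding and outcome measurement, says that "if surgeons express any complaint about muscle tone (the muscle tone: grade 3), rescue rocuronium 5 mg will be administered"; any body movement is the other trigger. Neither trigger is limited to one stage of surgery, and in this place the rule is not limited to one arm. The same triggers reappear in the Group RB paragraph as exceptions to the statement that "muscle relaxants will not be injected any more throughout the surgery except the following situations".

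**Recording.** In both places "the number of body movements and rescue rocuronium administration (dose) will be recorded". The reason for rescue, the tone grade and the time are not named.

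**Analysis.** The SAP covers "the muscle tone of each patient scaled by surgeons, assessed using a 3-point scale", gives no time point, and compares the arms by chi-squared or Fisher's exact test. It says nothing about patients without screws or patients rescued before scoring.

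**The concern.** There are two separate gaps.

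First, an eligible patient who has no pedicle screws never reaches the scoring moment. The scoring rule, the eligibility rule and the SAP's inclusion of each patient cannot all be followed for that patient, and no fallback is given.

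Second, the protocol treats grade 3 as something a surgeon may declare at any stage, but the outcome is read at one stage. A grade-3 complaint during exposure or retraction leads to rescue, and the score is taken afterwards. Rescue for movement can also come first and alter a later tone score. Group RB is reversed 10 minutes after being turned prone and then receives relaxant only as rescue, while Group DB is kept deeply blocked to the end of surgery. Early grade-3 episodes should therefore fall mainly in RB.

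At stake is one of the three operating-condition outcomes in hypothesis (2). The likely direction is dilution: a true advantage of deep block on tone could be understated or missed.

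**Working it through.** **1. The plan's own figure.** The only sample size stated is for the primary endpoint, peak inspiratory pressure.

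- Pooled SD = √((2.9² + 3.0²)/2) = 2.950, so d = (20.7 − 18.8)/2.950 = 0.644.
- A two-sided t-test at 0.05 with power 0.80 needs 38.8, that is 39 per group, as stated.
- 39 × 1.15 = 44.85, which rounds up to the stated 45.

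No power is stated for muscle tone. I use 39 per arm below as the planned evaluable number.

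**2. What happens to each kind of patient under the text as written.**

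| Patient | Score under 1.1 | Determined by the documents? |
|---|---|---|
| Screws, no rescue before insertion | Grade at insertion | Yes |
| Screws, grade 3 first noted at insertion | Grade 3, then rescue | Yes, so it is kept |
| Screws, grade 3 called and rescued earlier | Grade at insertion, after rescue | Whether the earlier grade 3 counts is not stated |
| Screws, earlier rescue for movement | Grade at insertion, after rescue | Handling is not stated |
| No screws | None | No rule |

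**3. Possible size.** Everything in this step about tone is an assumption.

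- Worst grades 1/2/3: DB 70/25/5%, RB 45/30/25%.
- A fraction f of grade-3 episodes, in both arms, is rescued before scoring and then reads lower. The grade-3 share left is p₃(1 − f). At f = 25/50/75%, RB keeps 18.75/12.5/6.25% and DB keeps 3.75/2.5/1.25%, so the grade-3 difference shrinks from 20 points to 15/10/5.
- Two rules for the lower reading: down one grade (3 to 2), or grade 1 and grade 2 equally often.
- Test: chi-squared on the 2 × 3 table, two-sided 0.05, by simulation.

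| f | Power, down one grade | Power, grade 1 or 2 equally |
|---|---|---|
| 0 | 73% | 73% |
| 25% | 66% | 60% |
| 50% | 59% | 46% |
| 75% | 54% | 28% |

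The first rule costs less because it leaves the grade-1 contrast (70% against 45%) intact.

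For patients without screws, assume shares of 20% or 40% and no rescue effect: 39 × 0.8 = 31.2 and 39 × 0.6 = 23.4, so 31 or 23 per arm are scorable. Power is about 59% or 45%.

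I repeated all these settings with 200,000 simulated trials each. The chi-squared results were within 2 points of those above. Fisher's exact test, run for the settings in the table with 6,000 trials each, was within 3 points.

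**4. A second set of assumptions.** Compare only the proportion with grade 3, assumed 30% in RB and 5% in DB, 39 per arm, by a two-proportion power calculation.

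- No loss: 84%.
- 25/50/75% of grade-3 cases lowered in both arms: 70/50/27%.
- Lowered in RB only: 62/31/7%.
- 10/25/50% without screws leaves 35/29/20 per arm: 80/72/55%.

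The direction is the same in both sets; the amount depends heavily on the assumptions.

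**The case against.** The strongest reply is that a single standard moment is a legitimate choice. Every patient is rated during the same surgical step. A worst grade over the operation is a different outcome, and it depends on how long surgery lasts and how readily the surgeon comments. This is a fair trade-off, and it supports keeping the screw-insertion grade as a supplementary result. It does not supply a score for patients without screws or say how earlier grade-3 complaints count.

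A second reply is that naming screw insertion suggests the team expected instrumented cases. That may be so. The gap would then reduce to an eligibility criterion that was left out, and the share of unscored patients could be nil.

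A reader might infer that the worst tone values are removed before scoring. The documents do not support that. Grade 3 first noted at insertion can be scored and then treated. Nothing says that the rescue dose lowers the grade, or for how long. The absence of a time point in the flowchart and SAP even leaves open whether tone is graded once or throughout.

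A reader might also infer that affected patients can be picked out from the rescue dose already recorded. They cannot be picked out reliably, because movement triggers the same rescue and neither the reason nor the time is named as recorded.

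Finally, tone is one of seven secondary outcomes, and the expected bias would not create a false benefit for deep block. Both statements stand, and they limit the importance of the point.

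**Conclusion.** The point holds as a defect in the definition of a secondary outcome. As written, eligible patients without screws have no tone score, and grade-3 episodes before screw insertion may go uncounted or be followed by a score altered by rescue. If these fall mainly in Group RB, as the two regimens suggest, the comparison is biased toward no difference. Missing scores in patients without screws would mainly cost precision, provided that the decision to use screws does not depend on allocation.

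The size cannot be fixed from the documents. Under the first set of assumptions, early rescue takes power from about 73% to somewhere between 66% and 28%, and the low end requires both a high share of early rescue and a large drop in grade. None of these figures should be quoted without its assumptions.

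The primary endpoint and its sample size are untouched: "Primary endpoint in this study is mean value of peak inspiratory pressure during the surgery".

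**What to change.** Reconcile Protocol 1.1, 1.3 and 1.5 with the SAP's analysis paragraph as follows.

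1. Define muscle tone for every patient as the surgeon's worst grade over a stated operative window, for example from retractor placement to closure.
2. Count any tone complaint in that window that triggered rescue as grade 3.
3. Keep the grade at screw insertion as a supplementary result in instrumented cases.
4. Record the reason, tone grade and time of each rescue, in addition to the dose and the number of movements.
5. Repeat the definition in the SAP, including the window and the handling of rescued patients.

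The cost is a revised outcome definition and a few extra fields on the case-report form. The statistical price is an outcome that depends somewhat on length of surgery and on how often surgeons comment; the supplementary screw-insertion result helps to show whether that matters. The rescue rule itself is not part of this change, and the enrolment target stays at 90.

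### The adverse-event window opens after surgery, so early events after sugammadex are probably counted in group DB but largely missed in group RB

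*Protocol*

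**What the plan says.** Protocol section 1.1 lists adverse events as secondary outcome 8: "Adverse Events [Time Frame: during the postoperative 24 hours". The flowchart in section 1.4 places them under postoperative assessment. The SAP compares their incidence between groups by a chi-squared or Fisher's exact test.

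Both arms receive sugammadex, at different times (section 1.5, NMB):

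- **Group RB:** it is given "to reverse the NMB 10 min after position change (10 min after placing the patient prone". For the end of the operation the flowchart shows "No reversal agent", with a different agent only if the TOF ratio is too low. The intra-operative dose is thus RB's only planned sugammadex exposure.
- **Group DB:** deep block is kept "until the end of surgery and the reversal of NMB will be performed by sugammadex 4 mg/kg".

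On assessment, section 1.5 says that "after the end of surgery, a blinded, independent investigator will assess the patients during the emergence and recovery phases". The anaesthesiologists who manage the patient during surgery are not blinded.

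Among the exclusion criteria, section 1.3 lists "The patients who will have hemodynamic instability", defined by a blood-pressure change of more than 30% lasting more than 5 minutes, and blood loss above 1 L during surgery.

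**The concern.** A short safety window is usually a matter of scope, because whatever it omits is omitted from both arms alike. Here the time of the sugammadex dose is fixed by the arm, so one window falls differently on the same drug. In DB it opens at or close to the dose. In RB it opens only after the rest of the operation has passed.

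If the early event risk per dose were identical, DB would still show more counted events. Randomisation and a blinded assessor cannot correct this, because the RB events are never recorded as adverse events.

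The exclusion in section 1.3 may add to the imbalance. Read literally, a haemodynamic reaction to RB's intra-operative dose could remove the patient. The same reaction after DB's dose at the end of surgery might fall outside an intra-operative rule and be counted.

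At stake is the adverse-event comparison, a secondary outcome.

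**Working it through.** **The plan's own figures.** The plan gives no adverse-event rate, event list or power for this outcome, so there is nothing to reproduce on the point itself. The SAP's sample size does reproduce: pooled SD = √((2.9² + 3.0²)/2) = 2.95; d = (20.7 − 18.8)/2.95 = 0.644; a two-sided t-test at 0.05 with power 0.80 needs 38.84, hence 39 per group. Adverse events do not enter it. Only the 45 enrolled per group is used below.

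**Step 1: time between dose and window.** Section 1.3 requires an operation of more than 1 hour ("1 hour and prone position under TIVA"). If surgery starts near prone positioning (an assumption), the RB dose comes about 10 minutes in, so at least about 60 − 10 = 50 minutes after it are uncovered. In DB the gap is about 0 if the postoperative period starts at the end of surgery. Assessment during emergence supports that reading, but no start is stated.

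**Step 2: counted risk in each arm.** Assumptions, since the documents give no rates:

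- an early risk *e* of 2%, 5% or 10% per dose, equal in both arms;
- a later postoperative risk *b* of 10%, equal in both arms and independent of early events;
- early events in RB resolve before the window opens, and all early events in DB are counted;
- all 45 patients per arm are analysed.

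Counted risk in RB = *b*. Counted risk in DB = 1 − (1 − *b*)(1 − *e*). Spurious excess = *e*(1 − *b*).

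| *e* | DB counted | RB counted | Spurious DB excess | RB patients missed, of 45 |
|---|---|---|---|---|
| 2% | 1 − 0.90 × 0.98 = 11.8% | 10% | 1.8 points | 0.8 |
| 5% | 1 − 0.90 × 0.95 = 14.5% | 10% | 4.5 points | 2.0 |
| 10% | 1 − 0.90 × 0.90 = 19.0% | 10% | 9.0 points | 4.1 |

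With *b* from 5% to 20%, the excess runs from 0.02 × 0.80 = 1.6 points to 0.10 × 0.95 = 9.5 points.

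**Step 3: chance of a falsely significant DB excess.** Sum the binomial probabilities over all pairs of counts (45 v 45) in which DB exceeds RB and the two-sided Fisher p is below 0.05.

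| *b* | *e* = 0 | *e* = 2% | *e* = 5% | *e* = 10% |
|---|---|---|---|---|
| 10% | 1.0% | 2.2% | 5.3% | 14.9% |
| 20% | 1.3% | 2.1% | 3.9% | 9.2% |
| 30% | 1.5% | 2.1% | 3.5% | 7.3% |

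The estimate is shifted against DB at every non-zero early risk. False significance becomes material only towards the top of the assumed range, and it weakens as the background risk rises.

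**The case against.** The best defence is that outcome 8 is a postoperative outcome by design. None of the protocol's three hypotheses concerns safety, the clock is the same in both arms, and the timing of sugammadex is part of each strategy. Incidence in the 24 hours after surgery is then a legitimate comparison of strategies. This stands for events that arise only after surgery. It does not stand if the result is read as whole-procedure safety or as a reaction rate to the drug.

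Three stronger readings are tempting, and the documents do not support them:

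- **A reader might infer that intra-operative harm in RB goes unseen.** It does not. Peak inspiratory pressure, retractor pressure, movements, bleeding and muscle tone are all intra-operative outcomes compared in the SAP, and rescue rocuronium is recorded. What goes uncounted is early reactions to sugammadex and other unlisted intra-operative events.
- **A reader might infer that no safety statement is possible.** One about the postoperative period still is.
- **A reader might compute a much larger false-positive rate.** With *e* = 10% and no other adverse events in either arm, a significant result needs 6 v 0 (p = 0.026; 5 v 0 gives 0.056), which happens in 29% of trials. An all-event incidence with no background events is implausible, and step 3 shows the rate falling to 15%, 9% and 7% with backgrounds of 10%, 20% and 30%.

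Two further objections stand in part. Full capture in DB is an inference: if the postoperative period began at arrival in the PACU, early DB events could be lost too. And widening the window brings in events recorded by unblinded staff, which the fix has to allow for.

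**Conclusion.** The concern holds in a limited form. Following the stated window counts early post-sugammadex events unequally by arm, in the direction that makes DB look worse. Under the assumptions in step 2, the distortion is 1.8 to 9.0 percentage points, with a falsely significant DB excess in about 2% to 15% of trials, against about 1% with no early events. The direction follows from the documents, provided that the postoperative period starts at the end of surgery; the size does not, because they give no rates. That adverse events are not recorded during surgery is judged from the text available for review. The priority is low to moderate.

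**What to change.** 1. In section 1.1, let outcome 8 run from induction of anaesthesia until 24 hours after the end of surgery in both arms, with the time of each event recorded. State when the postoperative period begins.
2. In the SAP, compare whole-period incidence, and also report intra-operative and postoperative events separately. Keep the blinded postoperative comparison as its own line.
3. Because unblinded anaesthesiologists would record the intra-operative events, use objective definitions fixed in advance and based on the existing ECG, oximetry and blood-pressure monitoring. State the remaining limitation in the report.
4. Reconcile the section 1.3 exclusion for haemodynamic instability and blood loss above 1 L during surgery with safety reporting, so that such events in randomised patients are reported by arm whatever the analysis set.

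The cost is revised wording in the outcome list and SAP, a short set of event definitions, and case-report-form fields for event and time. Item 4 also needs a decision on how the exclusion applies after randomisation. No extra monitoring or change of treatment is involved. The main downside is the mix of blinded and unblinded ascertainment in the whole-period figure, which is why the separate lines matter.
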